7.3.2. Potential Drug Interactions with Atezolizumab

Cytochrome P450 enzymes, as well as conjugation/glucuronidation reactions, are not involved in the metabolism of atezolizumab. No drug interaction studies for atezolizumab have been conducted. There are no known interactions with other medicinal products or other form of interactions. For additional details refer to the local prescribing information and the atezolizumab Investigator's Brochure.

7.3.3. Potential Drug Interactions with Sorafenib

Concomitant use of strong CYP3A4 inducers (such as, carbamazepine, dexamethasone, phenobarbital, phenytoin, rifampin, rifabutin, St. John's wort), should be avoided when possible, because these drugs can decrease the systemic exposure to sorafenib. Bleeding and INR elevations have been reported in patients receiving both warfarin and sorafenib; subjects in the sorafenib comparator arm taking concomitant warfarin should be monitored for changes in PT and INR and for clinical bleeding episodes. For additional details refer to the local prescribing information appropriate to the local site location.

8. SAFETY

8.1. Adverse Events and Laboratory Abnormalities

8.1.1. Adverse Events

An AE is any untoward medical occurrence in a patient or clinical investigation subject who has been enrolled in a clinical study and who may have been administered an investigational product, regardless of whether or not the event is assessed as related to the study treatment. An AE can therefore be any unfavorable and unintended sign (including an abnormal laboratory finding), symptom, or disease temporally associated with the use of an investigational product, regardless of whether or not the event is assessed as related to the investigational product. This requirement includes specific events or symptoms associated with cancer progression or general clinical deterioration to ensure potential toxicities are not overlooked. Radiographic progression without associated clinical sequelae is not considered an AE; terms such as ‘disease progression’ should be avoided. Pre-existing medical conditions that worsen during a study will be recorded as AEs. Abnormal laboratory values, ECG findings, or vital signs are to be recorded as AEs if they meet the criteria described in [Section 8.1.2](#).

All untoward events that occur after informed consent through 30 days (100 days for SAEs and AESIs) after the date of the decision to permanently discontinue study treatment (defined as the later of the date of the decision to discontinue all study treatment or the date of the last dose of any study treatment) are to be recorded in the source documents by the investigational site.

At each scheduled and unscheduled visit, AEs are to be identified and assessed based upon study procedures, routine and symptom-directed clinical investigations, and subject query/report.

Assessment of the relationship of the AEs to study treatment by the investigator will be based on the following two definitions:

- **Not Related**: An event is assessed as not related to study treatment if it is attributable to another cause and/or there is no evidence to support a causal relationship.
- **Related**: An event is assessed as related to study treatment when there is a reasonable possibility that study treatment caused the event. Reasonable possibility means there is evidence to suggest a causal relationship between study treatment and the event. This event is called a suspected adverse reaction. A suspected adverse reaction implies a lesser degree of certainty about causality than adverse reaction, which means any AE caused by a drug.

8.1.2. Laboratory Abnormalities

All laboratory data required by this protocol and any other clinical investigations will be reviewed. Any abnormal value that leads to a change in subject management (eg, dose reduction or delay or requirement for additional medication or monitoring) or that is considered to be of clinical significance by the Investigator will be reported as an AE or SAE as appropriate, unless this value is consistent with the subject's present disease state or is consistent with values obtained prior to entry into the study.

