
Urinalysis (Dipstick or Routine per Institutional Standard)
 
 pH specific gravity ketones protein glucose nitrite urobilinogen leukocyte esterase blood 	
Microscopic Urine Examination
 
 Perform at the discretion of the investigator based on results or routine urinalysis or as clinically indicated 
Urine Chemistry
 
 24-hour urine protein: perform at the discretion of the investigator based on increases in UPCR from routine assessments 	
Pregnancy Blood Test (prior to first dose)
 
 β-human chorionic gonadotropin (β-HCG) 
Pregnancy Urine or Blood Test (after first dose of study treatment)
 
 β-human chorionic gonadotropin (β-HCG) 
Virology
 
 HIV test (if mandated by local regulation)

^a For women under the age of 55 years to confirm menopause as needed.

Table 3: Estimation of the Creatinine Clearance by Cockcroft and Gault

Based on serum creatinine in conventional units (mg/dL)

• Males: $(140 - \text{age}) \times \text{weight (kg)} / (\text{serum creatinine} \times 72)$• Females: $[(140 - \text{age}) \times \text{weight (kg)} / (\text{serum creatinine} \times 72)] \times 0.85$
Based on serum creatinine in SI units (μmol/L)

• Males: $[(140 - \text{age}) \times \text{weight (kg)} / (\text{serum creatinine})] \times 1.23$• Females: $[(140 - \text{age}) \times \text{weight (kg)} / (\text{serum creatinine})] \times 1.04$

Abnormalities in any clinical laboratory test (including tests not required per protocol) that lead to a change in subject management (eg, dose interrupted or reduced, treatment discontinued, requirement for additional medication or monitoring) are considered clinically significant for the purposes of this study and should be reported as AEs. If laboratory values constitute part of an event that meets criteria defining it as serious, the event (with associated laboratory values) needs to be reported as an SAE (see [Section 8.2](#)).

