6.6.2.4. Management of Hepatobiliary Adverse Events

As this study will be evaluating subjects with advanced HCC, hepatobiliary AEs are expected to occur relatively frequently.

Elevations of aminotransferases and bilirubin have been observed during treatment with some anticancer therapies including cabozantinib, atezolizumab, and sorafenib. Modifications of study treatment may be appropriate to address these events, and management guidance for these agents in response to increases in aminotransferases and bilirubin is provided in this section.

General Guidance for Aminotransferase and Bilirubin Abnormalities

Patients with advanced liver cancer may have elevations of aminotransferases (ALT and AST) or bilirubin due to their disease. As such, subjects on this study may enroll with elevations of AST/ALT up to 5 \times ULN at baseline. It is recommended that subjects with elevations of ALT, AST, and/or bilirubin have more frequent laboratory monitoring of these parameters.

Evaluation of subjects with elevated transaminases or total bilirubin should be individualized and guided by the presence of specific risk factors such as illnesses which affect liver function (eg, infectious and non-infectious causes of hepatitis, liver cirrhosis, thrombosis of portal or hepatic vein), concomitant hepatotoxic medication, alcohol consumption, and cancer related causes. If possible, hepatotoxic concomitant medications should be discontinued in subjects who develop increased values of ALT, AST, or bilirubin. For patients with elevated LFTs, concurrent medication, viral hepatitis, and toxic or neoplastic etiologies should be considered and addressed, as appropriate.

Subjects with right upper-quadrant abdominal pain and/or unexplained nausea or vomiting should have liver function tests (LFTs) performed immediately and reviewed before administration of the next dose of study drug.

Guidance for Management of Hepatotoxicity

Guidance is provided on management of hepatotoxicity related to atezolizumab in [Table 28](#) and to cabozantinib in [Table 29](#).

Table 28: Management Guidelines for Hepatic Events Associated with Atezolizumab

Severity of Event	Management

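### Protocol 5.8.5 and 8.1.2 give opposite instructions on reporting laboratory abnormalities that changed treatment, so capture of non-serious, non-AESI laboratory AEs depends on which section a site follows

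*Protocol*

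**What the plan says.** Protocol 5.8.5, in the paragraph after the creatinine clearance table, covers "Abnormalities in any clinical laboratory test (including tests not required per protocol) that lead to a change in subject management". Its examples are interrupting or reducing the dose, stopping treatment, and adding medication or monitoring. Such abnormalities "are considered clinically significant for the purposes of this study and should be reported as AEs". No exception is attached.

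Protocol 8.1.2 starts from the same trigger. "Any abnormal value that leads to a change in subject management", or one that the investigator considers clinically significant, is to be reported as an AE or SAE "unless this value is consistent with the subject's present disease state or is consistent with values obtained prior to entry into the study".

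Protocol 8.1.1 points sites to the second rule: "Abnormal laboratory values, ECG findings, or vital signs are to be recorded as AEs if they meet the criteria described in" Section 8.1.2. It does not mention 5.8.5. The same section also says "Pre-existing medical conditions that worsen during a study will be recorded as AEs" and, of the AE definition, "This requirement includes specific events or symptoms associated with cancer progression or general clinical deterioration to ensure potential toxicities are not overlooked".

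Protocol 6.6.2.4 notes that "Patients with advanced liver cancer may have elevations of aminotransferases (ALT and AST) or bilirubin due to their disease". Inclusion criterion 10f admits subjects with ALT and AST up to 5 x ULN.

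On the analysis side, SAP 8.1 builds the tables of AEs leading to a treatment change from the action-taken fields on the AE form. SAP 6.6 summarises by dose level only those modifications that are due to an AE.

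**The concern.** Two sections govern the same laboratory value and can require opposite entries on the AE form. The deciding judgement, whether a value fits the subject's disease state, belongs to an investigator who knows the treatment arm. In advanced HCC that judgement is often open for liver tests, and Protocol 6.6.1 itself names transaminase increases as an overlapping toxicity of cabozantinib and atezolizumab. Sites that follow different sections would report different AE counts from the same laboratory data. A value that is not reported as an AE also cannot appear in a table of AEs leading to a hold, a reduction or a discontinuation. Those tables are the main description of tolerability by arm.

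**Working it through.** The plan states no figure on this point, so the check sets the texts side by side and follows one case through them.

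1. **Trigger.** Both sections act on a laboratory abnormality that changes subject management. Their examples overlap: a dose change, added medication, added monitoring.

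2. **Outcome.** Under 5.8.5 the value is clinically significant by definition and should be reported. Under 8.1.2 it is reported unless it fits the disease state or pre-entry values. The exception in 8.1.2 qualifies the whole sentence, including values that changed management. The comparable ECG rule in Protocol 5.8.4 has no such exception.

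3. **Precedence.** No section ranks one rule over the other. The only cross-reference, in 8.1.1, leads to the rule with the exception.

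4. **Is any case left after the separate reporting routes?** Protocol 8.3 (Table 31) makes two hepatic categories AESIs, reportable whether or not serious:
   - potential DILI: ALT or AST above 3 x baseline, together with total bilirubin above 2 x ULN (at least 35% direct) or clinical jaundice;
   - hepatitis, including AST or ALT above 10 x ULN.

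   Treatment changes start lower. Table 28 withholds atezolizumab for rises up to 10 x ULN, starting above 3, 5 or 8 x ULN according to baseline. Table 29 interrupts cabozantinib from 5 x ULN when baseline is at most 3 x ULN.

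   Take a constructed case in the combination arm: baseline ALT 3 x ULN, rising to 8 x ULN, bilirubin normal, no jaundice, not serious, hepatitis not diagnosed.
   - Table 28: 8 lies above 5 and at or below 10, so atezolizumab is withheld.
   - Table 29: 8 is at least 5, so cabozantinib is interrupted.
   - AESI: 8 is below 10, and 8 / 3 = 2.67 x baseline is below 3 with no bilirubin or jaundice criterion, so neither category is met.
   - Protocol 5.8.5: report as an AE.
   - Protocol 8.1.2: no report, if the investigator judges the value consistent with the HCC.

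   The exposed set is therefore not empty.

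5. **Which outputs change?** Without an AE record, the case is absent from the TEAE tables and has no action-taken field for SAP 8.1. If the site does not regard the value as an AE, the hold is not one due to an AE for SAP 6.6. The ALT value still enters the SAP 8.4 grade and shift tables. The dosing interval and its reason are still on the CRF (Protocol 6.4), and exposure and dose intensity are still computed (SAP 6.5).

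6. **Size.** This would need, by arm, the number of laboratory values that changed management, the share of them outside the AESI and SAE routes, and the share for which the exception was used. The documents give none of the three.

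**The case against.** The strongest reply is that little of importance is lost. Potential DILI and hepatitis have a 24-hour AESI route. SAEs are reportable regardless of causal relationship (Protocol 8.2.1). Encephalopathy and hepatic failure are clinical events, which 8.1.2 does not govern. SAP 8.4 grades ALT, AST, ALP, bilirubin and albumin by program from central and local results and screens for Hy's Law, so those comparisons are the same whatever a site enters as an AE. SAP 5.2 tabulates reasons for discontinuation. All of this stands, and it confines the point to non-serious, non-AESI laboratory terms. It does not supply the relatedness or action taken that only an AE record carries.

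A second reply is that 8.1.1 already narrows the exception, because worsening conditions and progression-related events are to be recorded. The thresholds in Table 29 are also rises from baseline, so the limb on pre-entry values would seldom apply to them. This is fair, but the disease-state limb remains arguable, and 8.1.1 is the section that refers sites to it.

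A reader might also infer a size from the protocol's single-agent atezolizumab data in HCC: AST increased in 40.0% of 15 subjects and 47.6% of 21, bilirubin increased in 47.6% of 21. Waiving 10% to 30% of a 45% event in one arm would move incidence by 4.5 to 13.5 points (0.10 x 45 and 0.30 x 45). The documents do not support that figure. The incidences are all-grade and not limited to values that changed management, and the waiver share and its one-sidedness are assumptions.

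**Conclusion.** The contradiction is real and needs to be removed. It makes the capture of non-serious, non-AESI laboratory AEs that changed treatment depend on the section a site follows, and it carries into the three sets of AE-based tables named in SAP 8.1 and 6.6. Neither the size nor the direction of any difference between arms can be computed.

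Two wider readings are tempting and should not be adopted. One is that hepatic AEs in general hang on this wording; the AESI and SAE routes and the clinical hepatic events do not. The other is that an unreported AE erases the dose change; it removes only the attribution to an AE, since the change and its reason remain on the dosing form. No efficacy endpoint, alpha or event count is touched, and no formal safety comparison is planned.

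The conclusion assumes that the site instructions not included here, such as the CRF completion guidelines, do not already settle which section governs.

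**What to change.** Amend Protocol 8.1.2 to match 5.8.5. Any laboratory value that led to a change in subject management is reported as an AE, whatever its presumed cause. The exception is kept only for values that had no management consequence and have not worsened from baseline. This changes a reporting rule only; the thresholds and actions in Tables 28 and 29 are not affected.

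Send sites a clarification, and have them reconcile AE records against the reasons for dose change that Protocol 6.4 already collects. Any hold, reduction or discontinuation made for a laboratory value without a matching AE record is queried.

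The cost is a clarification letter or amendment text, a round of queries and some additional AE entries. The stated incidence of laboratory AEs may rise, and the study report should say so.

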8.2. Serious Adverse Events

8.2.1. Definitions

The SAE definition and reporting requirements are in accordance with the ICH Guideline for Clinical Safety Data Management: Definitions and Standards for Expedited Reporting, Topic E2A.

An SAE is defined as any untoward medical occurrence that at any dose:

- Results in death.
- Is immediately life-threatening (ie, in the opinion of the investigator, the AE places the subject at immediate risk of death; it does not include a reaction that, had it occurred in a more severe form, might have caused death).
- Requires inpatient hospitalization or results in prolongation of an existing hospitalization.
- Results in significant incapacity or substantial disruption of the ability to conduct normal life functions.
- Is a congenital anomaly or birth defect.
- Is an important medical event that may not be immediately life-threatening, result in death, or require hospitalization, but may be considered an SAE when, based upon appropriate medical judgment, it jeopardizes the subject or may require medical or surgical intervention to prevent one of the outcomes listed above.

As soon as an investigator becomes aware of an AE that meets the criteria for an SAE, the investigator will document the SAE to the extent that information is available.

SAEs, regardless of causal relationship, must be reported to the Sponsor or designee within 24 hours of the investigator's knowledge of the event by submitting the completed SAE report

form and any other pertinent SAE information as indicated on the SAE Reporting form (or in the SAE Reporting form Completion Guidelines) and confirming the report was received. Forms for reporting SAEs and contact information will be provided to the study sites.

SAEs that must be recorded on an SAE Reporting form include the following:

- All SAEs that occur after informed consent and through 100 days after the date of the decision to permanently discontinue study treatment (ie, the later of the date of the decision of the investigator to permanently discontinue study treatment or the date of the last dose of any study treatment taken by the subject) or the date the subject is deemed to be a screen failure.
- Any SAEs assessed as related to study treatment or study procedures, even if the SAE occurs more than 100 days after the date of the decision to permanently discontinue study treatment.

Note: If the subject does not meet the eligibility criteria during screening, then SAEs only need to be reported from the time the subject signs the informed consent until the day when the subject has been determined to not be eligible for study participation.

SAEs that occur after consent through 100 days after the date of the decision to permanently discontinue of study treatment must also be recorded on the CRF page.

The minimum information required for SAE reporting includes identity of Investigator, site number, subject number, and an event description. Other important information requiring timely reporting are the SAE term(s), the reason why the event is considered to be serious (ie, the seriousness criteria), and the Investigator's assessment of the relationship of the event to study treatment. Additional SAE information including medications or other therapeutic measures used to treat the event, action taken with the study treatment because of the event, and the outcome/resolution of the event will be recorded on the SAE form.

In all cases, the Investigator should continue to monitor the clinical situation and report all material facts relating to the progression or outcome of the SAE. Furthermore, the Investigator may be required to provide supplementary information as requested by the Sponsor's Drug Safety personnel or designee.

When reporting SAEs, the following additional points will be noted:

- When the diagnosis of an SAE is known or suspected, the Investigator will report the diagnosis or syndrome as the primary SAE term, rather than as signs or symptoms. Signs and symptoms may then be described in the event description.
- Death will not be reported as an SAE, but as an outcome of a specific SAE, unless the event preceding the death is unknown. Terms of “Unexplained Death” or “Death from unknown origin” may be used when the cause is unknown. In these circumstances the cause of death must be investigated and the diagnosis amended when the etiology has been identified. If an autopsy was performed, the autopsy report should be provided.
- While most hospitalizations necessitate reporting of an SAE, some hospitalizations do not require SAE reporting, as follows:
 - Elective or previously scheduled surgeries or procedures for preexisting conditions that have not worsened after initiation of treatment (eg, a previously scheduled ventral hernia repair). SAEs must, however, be reported for any surgical or procedural complication resulting in prolongation of the hospitalization.
 - Prespecified study hospitalizations for observation.
 - Events that result in hospital stays of fewer than 24 hours and that do not require admission (eg, an emergency room visit for hematuria that results in a diagnosis of cystitis and discharge to home on oral antibiotics).
- SAEs must be reported for any surgical or procedural complication resulting in prolongation of the hospitalization.

8.2.2. Regulatory Reporting

The Sponsor’s Drug Safety group (or designee) will process and evaluate all SAEs and AESIs as the reports are received. For each SAE received, the Sponsor will make a determination as to whether the criteria for expedited reporting to relevant regulatory authorities have been met.

The Sponsor’s Drug Safety group (or designee) will assess the expectedness of each SAE to the study treatment using the current reference safety information (RSI) for each study drug.

The Sponsor or its designee is responsible for reporting relevant SAEs to the relevant regulatory authorities, and participating investigators, in accordance with FDA regulations (21 Code of Federal Regulations [CFR] 312.32), ICH guidelines, European Clinical Trials Directive (Directive 2001/20/EC), and/or local regulatory requirements.

Reporting of SAEs by the Investigator to his or her IRB/ECs will be done in accordance with the standard operating procedures and policies of the IRB/EC. Adequate documentation must be maintained showing that the IRB/EC was properly notified.

8.3. Adverse Events of Special Interest

Adverse events of special interest (AESIs) consist of immune-mediated AEs associated with ICIs, cases of potential DILI, and suspected transmission of an infectious agent by the study treatment ([Table 31](#)).

AESIs will be reported to the Sponsor or designee using the SAE reporting form irrespective of whether the event is serious or nonserious; all AESIs must be reported within 24 hours using the SAE process as described in [Section 8.2](#).

Guidance for management of immune-mediated AEs associated is provided in [Section 6.6.2.2](#) and can also be found in the local prescribing information and Investigator's Brochure for atezolizumab.

Table 31: Adverse Events of Special Interest

Category	Event
DILI	
Cases of potential DILI that include an elevated ALT or AST in combination with either an elevated bilirubin or clinical jaundice, as defined by Hy's Law and based on the following observations:
Treatment-emergent ALT or AST $> 3 \times$ baseline value in combination with total bilirubin $> 2 \times$ ULN (of which $\geq 35\%$ is direct bilirubin)Treatment-emergent ALT or AST $> 3 \times$ baseline value in combination with clinical jaundice
Other	
Suspected transmission of an infectious agent by the study treatment, as defined below
Any organism, virus, or infectious particle (eg, prion protein transmitting transmissible spongiform encephalopathy), pathogenic or non-pathogenic, is considered an infectious agent. A transmission of an infectious agent may be suspected from clinical symptoms or laboratory findings that indicate an infection in a patient exposed to a medicinal product. This term applies only when a contamination of study treatment is suspected.
irAE	
Pneumonitis
irAE	
Colitis
irAE	
Endocrinopathies: diabetes mellitus, pancreatitis, adrenal insufficiency, hyperthyroidism, and hypophysitis
irAE	
Hepatitis, including AST or ALT $> 10 \times$ ULN
irAE	
Systemic lupus erythematosus
irAE	
Neurological disorders: Guillain-Barré syndrome, myasthenic syndrome or myasthenia gravis, meningoencephalitis, myelitis, and facial paresis
irAE	
Events suggestive of hypersensitivity, infusion-related reactions, cytokine release syndrome, influenza-like illness, hemophagocytic lymphohistiocytosis, and macrophage activation syndrome
irAE	
Nephritis
irAE	
Ocular toxicities (eg, uveitis, retinitis)
irAE	
Myositis
irAE	
Myopathies, including rhabdomyolysis
irAE	
\geq Grade 2 cardiac disorders
irAE	
Vasculitis
irAE	
Severe cutaneous reactions (eg, Stevens-Johnson syndrome, bullous dermatitis, toxic epidermal necrolysis)

ALT, alanine aminotransferase; AST, aspartate aminotransferase; DILI, drug-induced liver injury; irAE, immune-related adverse event; ULN, upper limit of normal.

